4.2.4. Definition of Dose-limiting Toxicity

The occurrence of any of the following toxicities during Cycle 1 will be considered a DLT, if assessed by the Investigator to be possibly, probably, or definitely related to study treatment administration.

1. Grade 4 nonhematologic toxicity (not laboratory)
2. Grade 4 hematologic toxicity lasting \geq 7 days, except thrombocytopenia:
 - Grade 4 thrombocytopenia of any duration
 - Grade 3 thrombocytopenia associated with clinically significant bleeding
3. Any nonhematologic AE Grade \geq 3 in severity should be considered a DLT, with the following exceptions: Grade 3 fatigue lasting \leq 3 days; Grade 3 diarrhea, nausea, or vomiting without use of antiemetics or antidiarrheals per standard of care; Grade 3 rash without use of corticosteroids or anti-inflammatory agents per standard of care
4. Any Grade 3 or Grade 4 nonhematologic laboratory value if:
 - Clinically significant medical intervention is required to treat the patient, or
 - The abnormality leads to hospitalization, or
 - The abnormality persists for $>$ 1 week, or
 - The abnormality results in a drug-induced liver injury (DILI)
 - Exceptions: clinically nonsignificant, treatable, or reversible laboratory abnormalities including liver function tests, uric acid, etc.
5. Febrile neutropenia Grade 3 or Grade 4:

- Grade 3 is defined as absolute neutrophil count (ANC) $< 1000/\text{mm}^3$ with a single temperature of $> 38.3^\circ\text{C}$ (101°F) or a sustained temperature of $\geq 38^\circ\text{C}$ (100.4°F) for more than 1 hour
- Grade 4 is defined as ANC $< 1000/\text{mm}^3$ with a single temperature of $> 38.3^\circ\text{C}$ (101°F) or a sustained temperature of $\geq 38^\circ\text{C}$ (100.4°F) for more than 1 hour, with life-threatening consequences and urgent intervention indicated

6. Sepsis, severe abscesses and/or ulcerations requiring surgical management
7. Prolonged delay (> 2 weeks) in initiating Cycle 2 due to treatment-related toxicity
8. Investigator decision to discontinue study treatment for a treatment-related toxicity during Cycle 1
9. Missing $> 33\%$ of study drug doses as a result of Grade 3 drug-related AE(s) during the first cycle
10. Grade 5 toxicity

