--	--

	
In both arms, the escalation schedule may be adjusted based on PK, PD, and safety data emerging throughout the study to determine the MTD/RP2D.
 
In both study arms, each cohort will initially comprise 3 patients (a Sentinel patient and 2 non-Sentinel patients), with subsequent dose level investigation governed by the mTPI algorithm in accordance with protocol-mandated criteria.
 
Once the RP2D of Arm 2 is determined, up to 20 additional patients may be enrolled in the RP2D cohort to fully characterize the safety profile of SYNB1891 in combination with atezolizumab.
 
Definition of Dose-limiting Toxicity
 
The occurrence of protocol-specified toxicities during Cycle 1 (e.g., certain Grade 3/4 laboratory values; sepsis; or toxicity resulting in death, discontinuation of Cycle 1, or delay of Cycle 2; see Section 4.2.4) will be considered a DLT, if assessed by the Investigator to be possibly, probably, or definitely related to study treatment administration.

Duration of Study Participation	
The maximum time of study participation for a patient is up to 26 months, including the screening period (up to 28 days), treatment administration period (up to 24 months), and safety follow-up period (30 ± 5 days after the last dose).
 
Patients in Arm 1 will receive an initial 4 cycles of SYNB1891. Patients who do not have progressive disease at the end of Cycle 4 may receive additional cycles of SYNB1891 for up to 24 months (i.e., Cycles 5 to 35) after the initial dose of study treatment until documentation of progressive disease or other discontinuation criteria, satisfaction of a predefined study stopping rule, or no eligible lesions remain.
 
Patients in Arm 2 will receive an initial 4 cycles of SYNB1891 and atezolizumab. Arm 2 patients who do not have progressive disease at the end of Cycle 4 on combination therapy may receive additional cycles of SYNB1891 and atezolizumab for up to 24 months (i.e., Cycles 5 to 35) after the initial dose of study treatment until documentation of progressive disease or other discontinuation criteria, satisfaction of a predefined study stopping rule, or no eligible lesions remain.

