4.2. Study Dosing Regimens

4.2.1. Treatments Administered

Patients enrolled to Arm 1 may receive up to four 21-day cycles of SYNB1891 monotherapy. On Days 1, 8, and 15 of Cycle 1 and Day 1 of Cycles 2 through 4, patients will receive an i.t. injection of SYNB1891 into an eligible lesion. If the initial eligible lesion undergoes complete regression and is no longer injectable (at the discretion of the Investigator), a subsequent eligible lesion (until no more eligible lesions remain) may be injected.

At the end of Cycle 4, patients in Arm 1 who do not have progressive disease (i.e., those who achieve and sustain complete response [CR], partial response [PR], or stable disease [SD]) may receive additional cycles of SYNB1891 administered by i.t. injection on Day 1 of each cycle for up to 24 months (i.e., Cycles 5 to 35) after the initial dose of study treatment until documentation of progressive disease or other discontinuation criteria, satisfaction of a predefined study stopping rule, or no eligible lesions remain.

Patients enrolled to Arm 2 may receive up to four 21-day cycles with SYNB1891 administered by i.t. injection into an eligible lesion on Days 1, 8, and 15 of Cycle 1 and Day 1 of Cycles 2 through 4. In addition, atezolizumab will be administered in accordance with its recommended dose and schedule (1200 mg IV Q3W) on Day 1 of each of the 4 planned cycles. On days when atezolizumab and SYNB1891 are both administered, SYNB1891 will be administered first, followed by at least 1 hour of observation prior to the atezolizumab infusion. Patients in Arm 2 who do not have progressive disease (i.e., those who achieve and sustain CR, PR, or SD) at the end of Cycle 4 on combination therapy may receive additional cycles of SYNB1891 and atezolizumab for up to 24 months (i.e., Cycles 5 to 35) after the initial dose of study treatment until documentation of progressive disease or other discontinuation criteria, satisfaction of a predefined study stopping rule, or no eligible lesions remain.

Locating and/or injecting the lesion may be performed using guided imaging at the discretion of the Investigator.

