- Review of the safety data for the first patient in a cohort (Sentinel patient) must be completed on or after Day 7 before the remaining 2 patients (non-Sentinel) in that cohort may be dosed (these 2 patients may be dosed concurrently). Observation of DLT(s) in a Sentinel patient will not necessarily preclude enrollment of subsequent

patients at the same dose level; rather, DLTs occurring in Sentinel patients will be reviewed individually by the SRC (consisting of the Sponsor Medical Monitor, the CRO Medical Monitor, all active Investigators, and other study personnel as needed) to determine appropriate dosing for subsequent patients.

- After all patients in a cohort have been assessed for DLTs (i.e., after each patient either experiences a DLT or completes the end of Cycle 1 safety assessment, whichever occurs first), the SRC will review all available safety data from the cohort and determine whether to escalate to the next higher SYNB1891 dose, enroll additional patients at the current dose, de-escalate to the next lower dose, or declare that the study objectives or stopping rules have been met. The decision will be informed by the mTPI algorithm recommendation to achieve the targeted toxicity interval.
- Patients must either experience a DLT during Cycle 1 or receive at least 2 of the 3 planned SYNB1891 injections to be considered evaluable for DLT evaluations and contribute to dose-escalation decisions for a given cohort. Patients who withdraw from the study for any reason other than DLTs prior to receiving the second injection of SYNB1891 in Cycle 1 may be replaced.

Once the RP2D of Arm 2 is determined, up to 20 additional patients may be enrolled in the RP2D cohort to fully characterize the safety profile of SYNB1891 in combination with atezolizumab.

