9.7. Review of Safety Data

The Sponsor Medical Monitor in collaboration with the CRO Medical Monitor will be responsible for the ongoing review and evaluation of safety data, including AEs, clinical laboratory data, and any other safety evaluations, for the duration of the study.

The Sponsor will host Investigator teleconferences on a regular basis during the study. In addition, the Safety Review Committee (SRC; consisting of the Sponsor Medical Monitor, the CRO Medical Monitor, all active Investigators, and other study personnel as needed) will convene when all patients have completed the first cycle of study treatment in a given cohort and review all available safety information, including DLTs and all NCI CTCAE Grade 2 or higher toxicity data, as well as any other (e.g., PK/PD) data as indicated. Updated safety data on other ongoing patients, including data from later cycles, will be discussed as well.

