For lymphoma evaluated using LYRIC, the product of the perpendicular diameters (Longest Transverse Diameter \times Shortest Axis Perpendicular to Node) of the injected node will be listed per patient at each assessment visit. The change in the product of the perpendicular diameters will be summarized descriptively by comparing each follow up measurement to the baseline values. In addition, the percentage change of the product of the perpendicular diameters from baseline to the end of study for injected lesions will be displayed in waterfall plot by patient. A comparison of the percentage change between injected lesions and non-injected lesions (change in sum of the product of the perpendicular diameters) will also be presented in a waterfall plot for each patient.

VIII. Safety Analyses

Safety analyses will use data from the Safety population.

A. Treatment Exposure and Dosing Compliance

Exposure to SYNB1891 and atezolizumab will be summarized with descriptive statistics for the number of doses received, the number of cycles received, duration of dosing (weeks), total cumulative dose (cells/mL for SYNB1891, mg for atezolizumab). Duration of dosing is defined as the time from first dose of study drug in cycle 1 to the last dose of study drug in the last cycle a patient had.

The number of drug administrations with dose reduced, interrupted, and delayed will also be summarized descriptively by arm, cohort. In addition, the planned dosing date and the actual dosing date will be listed. Listings will be provided with the information from all the study drug administration eCRFs.

B. Dose Limiting Toxicities

Patients must have received at least one dose of the investigational product to be considered evaluable for the DLT evaluation and must have received at least 2 of the 3 planned SYNB1891 injections to contribute to dose-escalation decisions for a given cohort. DLTs will be determined for each patient through the end of Cycle 1. AEs and SAEs will be determined to be dose-limiting if they occur in this timeframe and meet the described criteria. AEs or SAEs experienced after the end of Cycle 1 will not be reported as DLTs but will be documented. Patients who experience a DLT (other than grade 5) will remain on the study to complete the safety evaluations and follow-up until resolution or stabilization of the DLT.

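### DLT criterion 7 and late-onset duration clauses resolve only after the end-of-Cycle-1 dose decision, and no rule says how a patient still open at that point is counted

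*Protocol*

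**What the plan says.** **Definition.** Protocol 4.2.4 states that "The occurrence of any of the following toxicities during Cycle 1 will be considered a DLT", provided the investigator judges it at least possibly related. Item 7 of the list is "Prolonged delay (> 2 weeks) in initiating Cycle 2 due to treatment-related toxicity". The synopsis likewise puts under Cycle 1 toxicities "toxicity resulting in death, discontinuation of Cycle 1, or delay of Cycle 2". Two other items depend on duration. Under item 2, Grade 4 hematologic toxicity other than thrombocytopenia counts from 7 days. Under item 4, a Grade 3 or 4 nonhematologic laboratory value counts, among other routes, if it lasts more than 1 week.

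**Timing of the decision.** In Protocol 4.2.3 the Safety Review Committee (SRC) decides once the whole cohort has been assessed, meaning "after each patient either experiences a DLT or completes the end of Cycle 1 safety assessment, whichever occurs first". Protocol 9.7 says the committee "will convene when all patients have completed the first cycle of study treatment in a given cohort". SAP VIII.B adds: "AEs or SAEs experienced after the end of Cycle 1 will not be reported as DLTs but will be documented". The safety paragraph of the protocol synopsis says the same.

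**Calendar.** Protocol 4.2.1: "Patients enrolled to Arm 1 may receive up to four 21-day cycles of SYNB1891 monotherapy". Injections are given "On Days 1, 8, and 15 of Cycle 1 and Day 1 of Cycles 2 through 4".

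**Existing limit on open patients.** Protocol 4.2.3 caps the number of enrolled patients who are not yet fully evaluable for DLT, by counting diagonal steps in Table 1 to the first unacceptably toxic cell. It does not say that a patient on hold at the end of Cycle 1 belongs to that group.

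**The concern.** The DLT count is both the input to every mTPI decision and the primary endpoint. A criterion that becomes observable only after the count has been used either never operates or has to change a number already acted on. The plan does not say which.

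For the three clauses at issue, an unresolved case that is entered in Table 1 without a DLT can only make the count too low. The stakes are those of a first-in-human trial with roughly 3-fold dose steps, in which completion of Cycle 1 evaluation in Arm 1 Cohort 4 also opens Arm 2.

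**Working it through.** **1. Reproduce Table 1 for small cohorts.** Inputs from the table footnote: target 0.30, prior Beta(1,1), ε1 = ε2 = 0.03. With x DLTs in n patients the posterior is Beta(1+x, 1+n−x). The decision is the interval with the largest probability per unit length among (0, 0.27), (0.27, 0.33) and (0.33, 1).

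- 0/3: 0.7160/0.27 = 2.65; 0.0825/0.06 = 1.37; 0.2015/0.67 = 0.30. Escalate (E).
- 1/3: 0.2959/0.27 = 1.10; 0.1056/0.06 = 1.76; 0.5985/0.67 = 0.89. Stay (S).
- 2/3: 0.0628/0.27 = 0.23; 0.0454/0.06 = 0.76; 0.8918/0.67 = 1.33. De-escalate (D).
- 3/3: P(p > 0.30) = 1 − 0.3⁴ = 0.992. Unacceptably toxic (DU), using a cutoff of 0.95. That cutoff is an assumption, as the documents do not state one.

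Done for all n from 3 to 6, this matches all 22 cells of Table 1.

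**2. When each clause can first be judged.** Cycle 1 is Days 1 to 21, so Cycle 2 Day 1 is planned for Day 22 (±1 day in the schedules). Durations use the SAP convention, stop − start + 1. An event needing L days can be judged by Day 21 only if onset is no later than Day 21 − L + 1.

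| Clause | Needed | Last onset judged by Day 21 | Open at Day 21 |
|---|---|---|---|
| Criterion 7 | more than 14 days after Day 22 | none | always; first true on Day 22 + 15 = Day 37 (36 to 38) |
| Grade 4 hematologic | L = 7 | Day 15 | onset Days 16–21 |
| Grade 3/4 laboratory, more than 1 week | L = 8 | Day 14 | onset Days 15–21 |

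The last two windows coincide with, or follow directly on, the Day 15 injection. Criterion 3 also has a duration element: Grade 3 fatigue of 3 days or less is exempt. Only onset on Days 19 to 21 is open there, and such an event is a DLT unless it proves short, so an open case need not be counted as DLT-free.

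**3. Against the decision date.** Criterion 7 is first observable 37 − 21 = 16 days after Cycle 1 ends. Protocol 4.2.3 and 9.7 place the assessment and the SRC meeting at the end of Cycle 1. Neither document provides a pending status, a longer window or a rule for reopening a count.

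**4. Effect of one uncounted DLT on Table 1** (true count, then count used):

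- n = 3: 1→0 turns S into E; 2→1 turns D into S; 3→2 turns DU into D.
- n = 4: 1→0 turns S into E; 3→2 turns DU into S.
- n = 5: 1→0 turns S into E; 3→2 turns D into S; 4→3 turns DU into D.
- n = 6: 2→1 turns S into E; 4→3 turns DU into S.

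**5. Who depends on these clauses alone.** Protocol 4.3.1 allows a new cycle to be withheld for neutrophils or platelets below its restart thresholds, or for nonhematologic toxicity that can be Grade 2. Cytopenia short of Grade 4, without bleeding or febrile neutropenia, and Grade 2 nonhematologic toxicity meet no severity-based DLT item. Criterion 8 covers discontinuation only during Cycle 1. For such patients criterion 7 may be the only route to a DLT.

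**6. Illustration only.** The share f of DLTs that become apparent only after Day 21 is not in the documents. If f applied to all DLTs and 0/3 always led to escalation, P(0 of 3 counted) = (1 − p(1−f))³:

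| True DLT rate p | f = 0 | f = 0.1 | f = 0.3 |
|---|---|---|---|
| 0.30 | 0.343 | 0.389 | 0.493 |
| 0.40 | 0.216 | 0.262 | 0.373 |
| 0.50 | 0.125 | 0.166 | 0.275 |

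This shows direction and sensitivity. It does not estimate the effect in this trial.

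**The case against.** The case for leaving the text alone has real weight.

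- **Status is not expressly closed at Day 21.** A reader might infer that the documents forbid late counting. They do not: the synopsis and SAP VIII.B exclude events experienced after Cycle 1, and a toxicity with Cycle 1 onset that later delays Cycle 2 is not clearly such an event. SAP VIII.B also refers back to Protocol 4.2.4. Later reclassification is undefined rather than barred. Equally, the schedules have no Day 21 visit, so the date of the end-of-Cycle-1 assessment is itself unclear when Cycle 2 is delayed. This stands.
- **Duration criteria mostly work.** A reader might infer that no duration-based criterion can be judged in time. Onset in roughly the first two weeks can be. Grade 4 thrombocytopenia counts at any duration, and the laboratory item has immediate alternatives such as hospitalization. This stands, and limits the point to late onset.
- **Overlap.** Many toxicities that hold Cycle 2 for over two weeks already qualify under another item, for example nonhematologic Grade 3 or higher. This stands.
- **SRC discretion.** The committee reviews all available safety data, sees Grade 2 or higher toxicity and later-cycle data, and is informed rather than bound by the algorithm. A patient on hold would be visible, so automatic escalation should not be inferred. This mitigates the dose decision, but discretion is not a counting rule and the primary endpoint is a count.
- **Final tables come later.** Criterion 7 status will be known by then, so bias in the final DLT percentage arises only if the exclusion of post-Cycle-1 events is read strictly. That is correct, and it is why the reading needs to be fixed in advance.

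**Conclusion.** The plan needs correcting here: one stated DLT criterion cannot operate under the stated assessment timing, and two duration clauses share the problem for late-onset events. A patient who is open at the end of Cycle 1 can be entered in Table 1 as DLT-free, and for these clauses the error can only lower the count.

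The supportable size is per patient: at n = 3, one uncounted DLT moves the recommendation one step in the permissive direction, and at n = 4 or 6 it can turn unacceptably toxic into stay. How often this would happen cannot be computed from the documents, so no percentage bias should be claimed.

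The calendar result assumes cycles on schedule, Cycle 1 ending on Day 21, and the SAP's inclusive day count.

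**What to change.** Reconcile the protocol synopsis (safety analysis), Protocol 4.2.3, 4.2.4 and 9.7, and SAP II and VIII.B, so that:

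1. A patient whose Cycle 2 is on hold for treatment-related toxicity, or whose Cycle-1-onset event is still running against a duration clause at the end of Cycle 1, is not yet fully evaluable under the existing diagonal rule. This lasts until the clause is met or can no longer be met. For criterion 7 that is about Day 37; Day 36 is exactly 14 days of delay and would release the patient too soon. For example, with one DLT in five resolved patients and a sixth open, the count is 1/5 (S), not 1/6 (E), until the sixth resolves.
2. A Cycle-1-onset toxicity that later meets the clause counts as a DLT, both in the Table 1 count and in the primary DLT table.
3. The text says how a patient is counted if treatment is stopped during the hold. Protocol 4.3.1 sets a 14-day recovery limit, while criterion 7 requires more than 2 weeks and criterion 8 stops at Cycle 1.

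The DLT criteria and the treatment rules are unchanged. The cost is wording in both documents and about two weeks' delay of the SRC decision, only in cohorts with such a patient.

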If a patient has multiple occurrences of an adverse event, the strongest level of relationship to study drug and the worst toxicity grade a patient experiences for a given AE will be used in these tables. No imputation will be performed for missing toxicity grade or causality data. The number and percentage of adverse events without relationship or toxicity grade values will be summarized under “Missing” category.

Adverse events that have missing onset dates will be considered as treatment emergent unless the stop date is known to be prior to the first administration of the study medication. If the adverse event onset date is partial, the date will be correlated as far as possible with the date of first dose of study medication. Adverse events will be assumed to be treatment-emergent, unless there is clear evidence (through comparison of partial dates) to suggest that the adverse event started prior to the first dose of study medication. Detailed imputation rules can be found in section V. If patients died during the study and experienced AEs at the time of death, the AEs that lead to death will use death date as the AE end date; otherwise, AEs that do not lead to death will be reported as ongoing.

The following TEAE summaries will be produced by arm and dose cohort, and overall:

- a. An overall summary of safety will summarize the numbers (and percentages) of patients with the following:
 - at least one AE and serious adverse event (SAE)
 - AEs related to each study drug
 - SAEs related to each study drug
 - AEs of Special Interest

- DLTs
- discontinued study drug (SYNB1891, atezolizumab, and overall) due to at least one AE
- AEs leading to death

b. Separate summaries of TEAEs by System Organ Class and Preferred Term, subset as follows:

- All TEAEs
- TEAEs related to each study drug separately (SYNB1891 and atezolizumab). This table will include TEAEs with a drug relationship of “Definitely Related”, “Probably Related” or “Possibly Related”. It will also include TEAEs with missing drug relationships. An AE reported by a patient more than once will be included in this table if at least one of the drug relationship is one of the categories listed here.
- All Serious TEAEs

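### DLT criterion 9 counts doses missed for Grade 3 events only, so a short Grade 4 cytopenia that costs an injection is scored DLT-free; the criterion's Arm 2 dose denominator is also undefined

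*Protocol*

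**What the plan says.** Criterion 9 of Protocol 4.2.4 applies when a patient misses more than 33% "of study drug doses as a result of Grade 3 drug-related AE(s) during the first cycle". Elsewhere in that list the higher grade is written out: criterion 3 covers Grade 3 and above, and criteria 4 and 5 name Grades 3 and 4. Criterion 2 covers "Grade 4 hematologic toxicity lasting" 7 days or more, with thrombocytopenia handled separately (Grade 4 at any duration, Grade 3 with clinically significant bleeding).

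Under Protocol 4.2.3 a patient contributes to dose decisions by having a DLT, or must "receive at least 2 of the 3 planned SYNB1891 injections to be considered evaluable for DLT evaluations".

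On the number of Cycle 1 doses, Protocol 4.2.1 says for Arm 1: "On Days 1, 8, and 15 of Cycle 1 and Day 1 of Cycles 2 through 4, patients will receive an i.t. injection". In Arm 2, SYNB1891 is "administered by i.t. injection into an eligible lesion on Days 1, 8, and 15 of Cycle 1"; atezolizumab adds one infusion per cycle, given on the first day. Protocol 6.1 defines *study treatment* as either or both agents. The term used in criterion 9, *study drug*, is not defined. SAP VIII.C tabulates patients who "discontinued study drug (SYNB1891, atezolizumab, and overall) due to at least one AE". SAP VIII.B refers back to Protocol 4.2.4 for the DLT definition and adds nothing on this wording.

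**The concern.** A toxicity rule should not score a worse event as less toxic. Criterion 9 is the only criterion that turns a missed dose within Cycle 1 into a DLT, and as written it stops at Grade 3. Where no other criterion picks up the Grade 4 version of an event, the ordering reverses.

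DLT incidence is the primary endpoint (Protocol 3.1, SAP II) and the input to the mTPI rules. A misordered or ambiguous criterion therefore affects both the reported percentage and the escalation recommendation. A percentage threshold with an unstated denominator adds a second risk: two investigators could score the same Arm 2 patient differently.

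**Working it through.** **1. Can the case arise?** Protocol 7.2.5.1 requires dosing-day laboratory values to meet the limits in 5.2.1.1, including a neutrophil count of at least 1500/µL (only platelets and hemoglobin are relaxed). Protocol 4.3.1 treats a Cycle 1 dose delayed by more than 2 days as missed. A short neutropenia can therefore cost an injection through the protocol's own rules.

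**2. Score a related, afebrile Grade 4 neutropenia of 6 days that costs one injection.** Assume that Cycle 2 is not delayed by more than 2 weeks and that treatment is not discontinued.

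- Criteria 1, 3 and 4: nonhematologic only. Not met.
- Criterion 2: 6 days is less than 7. Not met.
- Criterion 5: no fever. Not met.
- Criterion 6: no sepsis, abscess or ulceration. Not met.
- Criteria 7 and 8: excluded by assumption.
- Criterion 9: names Grade 3 only. Not met.
- Criterion 10: not Grade 5. Not met.

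The patient has received 2 of 3 injections, so is evaluable under Protocol 4.2.3 (and under SAP VIII.B), and enters Table 1 as DLT-free.

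**3. Score the same event at Grade 3 in Arm 1.** Doses missed / doses planned = 1/3 = 33.33%, which exceeds 33% by 0.33 percentage points. Criterion 9 is met and the patient is a DLT.

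**4. Effect of one reclassified patient in Table 1.**

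| Evaluable | DLTs | Decision |
|---|---|---|
| 3 | 0 to 1 | E to S |
| 3 | 1 to 2 | S to D |
| 3 | 2 to 3 | D to DU |
| 6 | 0 to 1 | E to E |
| 6 | 1 to 2 | E to S |
| 6 | 2 to 3 | S to S |
| 6 | 3 to 4 | S to DU |

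With 3 evaluable patients every reclassification changes the decision. With 6, two of the four shown do.

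**5. The threshold under each reading of *study drug doses*.** Cycle 1 has 3 SYNB1891 injections in each arm, and Arm 2 adds 1 atezolizumab infusion.

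| Reading | One missed injection, Arm 1 | One missed injection, Arm 2 |
|---|---|---|
| More than 33%, SYNB1891 only | 1/3 = 33.3%, DLT | 1/3 = 33.3%, DLT |
| More than 33%, both drugs pooled | 1/3 = 33.3%, DLT | 1/4 = 25%, not a DLT (2/4 = 50% is) |
| More than 33%, each drug separately | 1/3 = 33.3%, DLT | 1/3 = 33.3%, DLT (a missed infusion is 1/1 = 100%) |
| More than one third | 1/3 does not exceed 1/3, not a DLT | 1/3 or 1/4, not a DLT |

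Under the last reading two missed doses are needed in either arm (2/3 = 66.7%, or 2/4 = 50% if pooled).

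**The case against.** **The gap is small.** This stands. Criteria 1 to 5 already capture most Grade 4 events: nonhematologic toxicity, thrombocytopenia at any duration, other cytopenias of 7 days or more, and febrile neutropenia. The SYNB1891 events of special interest in Protocol 9.3 are all nonhematologic, and the documents give no expected cytopenia rate.

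**Bare Grade 3 may be shorthand for Grade 3 or higher.** Tables 6 and 10 do direct the reader to treat an event as Grade 3 when the row meant is labelled Grade 3 or higher. But three criteria in the DLT list itself spell out the higher grade, so the literal reading is the natural one there.

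**The Safety Review Committee sees everything.** Under Protocol 4.2.3 and 9.7 the mTPI output informs the decision, and the committee reviews all Grade 2 or higher toxicity. This can soften an escalation decision. It does not correct the reported DLT percentage.

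**Stronger readings that a reader might infer.** One is that a single missed injection is a DLT in Arm 1 but not in Arm 2, so the combination arm has the more lenient rule. That needs the two drugs' doses to be pooled, and the documents do not establish pooling. Criterion 9 does not name SYNB1891, and the SAP applies *study drug* to both agents, which gives pooling some support. But the SAP line lists the agents separately before the overall row and never forms a common dose denominator. SAP V.F dates the start of study drug by the first SYNB1891 dose. The neighbouring Cycle 1 rules (Protocol 4.2.3 and 4.3.1) count SYNB1891 only. Only an undetermined denominator is shown.

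Another is that a short Grade 4 nonhematologic laboratory value also escapes. That is doubtful: Protocol 9.6 records a laboratory abnormality as an AE when it leads to an action on dosing, and criterion 3 may then count it.

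**Conclusion.** The point holds in a limited form. As written, criterion 9 excludes events more severe than those it counts. For a related, afebrile, non-platelet Grade 4 cytopenia of under 7 days that costs one injection, no other criterion fills the gap. Such a patient is scored DLT-free, while the Grade 3 equivalent in Arm 1 is a DLT.

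The size is one Table 1 step per affected patient in a three-patient cohort. How often it would occur cannot be estimated from the documents.

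The one-injection comparison rests on reading the 33% threshold literally. If it means more than one third, a single missed injection is not a DLT at Grade 3 either, although criterion 9 would still omit Grade 4. In Arm 2 the comparison also depends on the denominator: with pooled doses (25%), one missed injection is not a DLT at either grade. These ambiguities are a second defect in the same sentence. They do not show that the two arms are held to different standards.

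**What to change.** Amend criterion 9 so that its grade range does not exclude events more severe than those it counts, for example by writing Grade 3 or higher. In the same sentence, state which drug's doses form the denominator in each arm, and replace the percentage with a count of missed doses. The sponsor should choose that count. Protocol 4.2.1, 4.2.3, 4.2.4, 4.3.1 and 6.1 then need to be reconciled on the terms used and on what is counted.

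The cost is one sentence in Protocol 4.2.4 and a check of the related sections. The SAP refers to 4.2.4 and would follow it. The downside is that a few more events may count as DLTs.
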